Protocol Title: Internet-based Cognitive Behavioral Therapy to Reduce Depressive Symptoms after Stroke Pilot/Feasibility Study

Short Title: Internet-based CBT for Depression after Stroke Pilot

Investigators:

[name]
[name]
[name]

Brief Description:

Stroke is one of the leading causes of death and disability in the United States, with estimated direct and indirect costs exceeding 70 billion dollars per year. Depression is common after stroke, occurring in approximately 25% of all patients. Depression has been associated with lower quality of life, higher mortality, increased healthcare utilization and higher costs. Cognitive behavioral therapy (CBT) interventions have been shown, in small studies, to both treat and prevent the development of post-stroke depression. CBT based interventions therefore have the potential to improve quality of life and reduce healthcare costs after stroke. Unfortunately, there are significant barriers to the widespread use of CBT in the stroke population, including limited access to licensed providers, high costs of treatment, and limited mobility. Alternative methods for delivering CBT have the potential to improve access and reduce costs and may make widespread dissemination of CBT based treatment possible. We aim to test the feasibility of an internet-based CBT (iCBT) program combined with a telephone/email based coaching service in patients with recent stroke. We will do this by partnering with Joyable. Joyable is an existing, commercially available iCBT program. Joyable's iCBT Program for Depression combines 42 brief online activities with a telephone/email based coaching service, which is designed to motivate and encourage individuals to complete the online modules.

Objectives:

1. Determine the feasibility of internet-based CBT in patients with recent ischemic stroke and depressive symptoms, by quantifying adherence to the program in a pilot population of 20 subjects.
2. Quantify changes in depressive symptoms and quality of life in subjects pre- and post-program participation, to provide preliminary evidence of the efficacy of internet-based CBT to improve outcomes after stroke.

Primary Outcome variables

The primary outcomes will be the number of activities in the iCBT program completed by participants and reduction in depressive symptoms, measured the 9-item Patient Health Questionnaire (PHQ-9).

Secondary Outcome variables

Secondary outcome variables will include: completion of the iCBT program, number of telephone/email based coaching interactions, quality of life, measured using the EuroQOL-5D

(EQ-5D), healthcare utilization, measured using the Stanford Health Care Utilization Survey, and subject satisfaction with the program.

Background

Depression after stroke

Depression is common after stroke, occurring in up to one-third of all stroke patients.¹ A recent American Heart Association (AHA) scientific statement on post-stroke depression highlighted the importance of this condition, noting that it was “under-recognized, under-investigated, and under-treated.”² Individuals with depression after stroke have been shown to have lower functional status and lower quality of life than those without depression, irrespective of stroke severity, although the independent contribution of depression on outcomes is still not fully understood.

Traditional Cognitive Behavioral Therapy

Cognitive behavioral therapy (CBT) is an effective treatment for common mood disorders. Studies have shown a beneficial effect of CBT for both the treatment and prevention of depression after stroke.^{3,4} There is also evidence suggesting that CBT may provide a more durable and lasting treatment effect than pharmacotherapy with selective serotonin reuptake inhibitors.⁵

Despite the promise of CBT, its role in routine clinical practice is limited. There are significant barriers to widespread use of CBT. First, access to experienced CBT practitioners is limited.⁶ Second, the time and travel requirements to complete a course of CBT, which may require 2-3 visits per week for 10-12 weeks, are onerous for many patients. This may be even more difficult for patients with mobility limitations, which are common after stroke. Third, the cost of CBT may be prohibitive, particularly if providers do not accept insurance.⁶ Finally, patients may be resistant to in-person CBT because of stigma or fear of sharing deeply personal feelings with a therapist.

Technology and CBT

Technology provides an exciting alternative to traditional CBT.⁶⁻⁸ Internet-based CBT has the potential to lower costs and improve accessibility. Internet-based CBT eliminates the challenges of finding a therapist and/or arranging transport to/from visits. There is also limited data to suggest that technology has the potential to reduce the stigma and fear associated with in-person therapy sessions, and subjects may actually be more likely to disclose symptoms when they believe they are interacting with a computer rather than a human.⁹

Although internet-based CBT interventions may provide a lower intensity of treatment than traditional in-person CBT, they still have the potential to be effective. An individual patient-data meta-analysis of 3876 subjects from 13 studies concluded that internet-based CBT is effective at treating depressive symptoms in general.¹⁰ Encouragingly Internet use is now common among older adults in the U.S. The Pew Research Center reported that in 2016 87% of 50-64 year olds and 64% of adults 65 years or older use the Internet.¹¹ The few studies of internet-based CBT interventions among older adults have demonstrated their efficacy in reducing depressive symptoms among adults 50 years or older and among adults 45 years or older with cardiovascular disease (CVD) or risk factors for CVD.^{12, 13 14} Thus, an Internet-based CBT intervention among stroke survivors has the potential to reduce depressive symptoms. However, because patients with stroke have experienced a structural brain injury and may have residual cognitive and physical disability, dedicated study within the stroke population is necessary.

Joyable: Internet-based CBT with personalized coaching

Joyable offers an iCBT program for Depression which is an 8-week, internet-based cognitive behavioral therapy (CBT) program for depression, developed alongside [name] PhD, a clinical psychologist with research expertise in the processes and outcomes of treatments for depression. Joyable users complete brief interactive modules (42 total activities) on a smartphone or computer. Most of these modules can be completed in 5-10 minutes and cover the core elements of CBT: psychoeducation, cognitive restructuring, and behavioral activation. In addition to its digital programs, users receive unlimited guidance and support from coaches via phone, text, and email. Coaches both respond to and proactively reach out to participants. They are trained extensively in motivational interviewing, with the goal of driving participants toward completion of the CBT program. Joyable's depression program has shown symptom reduction of 40%, as measured by the PHQ-9, with satisfaction and completion rates that exceed face-to-face therapy (unpublished data, from Joyable).

Joyable monitors the subjects' mood through weekly assessments of the PHQ-9. There are built-in escalation protocols, designed with [name], the former President of the American Association for Suicidology. Joyable identifies safety risks both through its software and through extensive training of coaches. All coaches are trained with how to respond to at-risk clients, including providing emotional support and informing clients about appropriate resources to support them, including the National Suicide Prevention Lifeline and Crisis Text Line. In urgent cases, Joyable can also connect clients with a licensed professional by phone.

Study Design

Design: A pilot single arm clinical trial is proposed. Adults (18 years or older) with ischemic stroke will be enrolled within 63 months of their event. All subjects will be enrolled in Joyable's iCBT program for Depression.

Duration: The study will plan to enroll 20 subjects. Each subject will be in the study for 90 days. The project will begin immediately after IRB approval. The study is expected to take approximately 1 year to complete.

Resources for human research protection: The clinical research section of the comprehensive stroke center at the University of Pennsylvania will conduct the study. This team has extensive experience conducting both observational and interventional studies in stroke patients. The clinical research team consists of four full time clinical research coordinators, 1 nurse practitioner, 3 vascular neurology fellows, 2 vascular neurology research fellows, and 7 vascular neurology attendings. All members of the clinical research team will be required to complete CITI training and maintain up to date certification while the study is underway. The research team will maintain training records, including copies of all pertinent certificates. Prior to initiation of the study, the research team will have an in-service session to review the study protocol and procedures in detail. While the study is underway, the research team will meet weekly to discuss the study, including enrollment, follow-up, and any other issues which may arise. [name] will be primarily responsible for overseeing the study.

Target Population: Adult patients hospitalized with ischemic stroke within the past 63 months.

Inclusion Criteria:

- Age \geq 18 years of age
- Acute ischemic stroke within the past 63 months

- Regular access to the internet, sufficient to allow a minimum of interactions with the internet daily, either through a personal smartphone or web-based internet browser.
- Subject is willing and able to participate in internet-based cognitive behavioral therapy
- Can participate in the program in English
- Willingness and ability to sign informed consent by the patient
- Symptoms of mild to moderately depressed mood, defined as a score of 5-19 on the Patient Health Questionnaire-9 at the time of study enrollment.

Exclusion Criteria

- Severely depressed patients, defined by a score of 20+ on the Patient Health Questionnaire-9 are excluded
- Patients with an active bipolar disorder diagnosis are excluded
- Patients with personality disorder diagnoses are excluded
- Patients with active suicidality or past suicide attempts are excluded
- History of schizophrenia or schizoaffective disorder
- Active participation in face-to-face psychotherapy prior to stroke
- Patients with a history of dementia are excluded
- Patients with aphasia, defined as a score of 1 or greater on NIH Stroke Scale Item 9 are excluded.
- Patients without regular internet access through a computer, tablet or smartphone are excluded.
- Subjects requiring long-term inpatient nursing care are excluded. For patients enrolled as inpatients, individuals being discharged to both home and acute rehab are eligible. Individuals being discharged to a skilled nursing facility or hospice are excluded.
- Expected life expectancy less than 6 months or other inability to comply with study follow-up.
- Pregnant women and prisoners are excluded

Vulnerable populations: Children, pregnant women, fetuses, neonates, and prisoners are not included in this research study.

Sample Size: 20 subjects will be enrolled.

Accrual: The comprehensive stroke center at the Hospital of the University of Pennsylvania (HUP) is a tertiary referral center for acute ischemic stroke, with annual case volumes of approximately 600 strokes per year on the inpatient stroke service. Additionally, the stroke team sees patients in the outpatient clinic both in follow-up from their acute hospitalization and in consultation to provide second opinions for patients treated elsewhere. Due to the broad inclusion criteria of this study, it is expected that many of the patients seen, both inpatient and outpatient, will be eligible for participation in this study. We expect that we will be able to enroll 1-2 patients per week and will complete enrollment within 6 months.

Recruitment: A stroke physician evaluates all patients with acute ischemic stroke who present to HUP. All stroke team physicians will be trained investigators in this study, and they will screen patients for eligibility during routine clinical care. Study physicians will also screen for potentially eligible subjects during outpatient clinic sessions. All eligible subjects will be informed of the study, and if they are interested in participation, a study physician will obtain informed consent. The original signed consent form will be kept in the study binder. A copy of

the signed consent form will be given to the patient and another copy will be placed in the medical record.

Procedures

Consent: A member of the study team will approach eligible patients. The consent form will be described in plain language. The patient will be given a hard copy of the consent form for their reference. Written informed consent will be obtained. Judgements about capacity to provide informed consent will be made by the physicians caring for the patient and the person obtaining informed consent. All patients with acute ischemic stroke received detailed neurologic assessments, including assessments of cognition, language function, neglect/anosognosia, and other domains of neurologic function. Additionally, during the consent process the subject will be asked open-ended questions about the study such as: "Would you explain to me what you think we are asking you to do?" and "what are the possible benefits and risks to you of participating in this study?" If either the clinical team feels that the patient cannot provide informed consent, or the patient's responses to these open-ended questions fail to demonstrate sufficient comprehension to provide informed consent, in the judgment of the investigator, the patient will be excluded from participation. The subject will have the ability to withdraw consent at any time.

Study Procedures:

Baseline

After consent is obtained, the Patient Health Questionnaire-9 (PHQ-9)¹⁵ will be administered to the subject. This is a simple, 9-item survey which has been validated to identify depression after stroke. Patients who score between 5-19 inclusive will be enrolled in the study. Subjects who score 0-4 or 20+ will receive education about post-stroke mood disorders and local psychiatry/psychology resources, including the contact information for regional crisis centers, but will not be enrolled. Subjects who screen 20+ will have their attending physician notified so that appropriate referrals or treatments can be initiated by the clinical team.

For patients who are enrolled, basic demographic and clinical information will be collected including: age, sex, race/ethnicity, past medical history (including history of hypertension, hyperlipidemia, coronary artery disease, chronic kidney disease, prior history of TIA/Stroke, prior history of anxiety, depression, or PTSD, other medical history), educational attainment, insurance status, marital status, number of people living in the home, medication history (current/prior use of an antidepressant medication), current/prior participation in psychotherapy or counseling for mental health problems, tobacco history (current smoker, former smoker, never smoker), alcohol use history (current alcohol use yes/no and if yes, number of drinks per week), stroke location, stroke mechanism (large vessel atherosclerosis, small vessel disease, cardioembolism, other, cryptogenic), discharge disposition (home, acute rehab).

Additional assessments will include the NIHSS, a structured neurologic examination used to quantify neurologic deficits,^{16, 17}, modified Rankin Scale,¹⁸ the Patient Health Questionnaire-9 (PHQ-9) to assess mood,¹⁵ and the abbreviated Duke Social Support Index.¹⁹ We will also ask the subject a series of questions regarding availability of internet and mobile device usage, including how they interact with the internet and frequency of internet use (See attached appendix).

After baseline data collection, the subjects will be enrolled in Joyable's iCBT program. For subjects who would like to participate in the program using their smartphone, the CBT application will be installed on their device and they will be encouraged to complete the initial

evaluation and activities at the time of enrollment. Subjects without their own device will be enrolled via a study specific tablet using the web-interface. Subjects will be given their login information and information on how to access the program via the internet and install the program on their mobile device. Subjects will be asked to complete the initial evaluation and CBT activities at the time of enrollment.

Joyable is a commercially available 8-week program that consists of 5-6 online activities per week, for a total of 42 activities. Most activities can be completed within approximately 5-10 minutes. Activities cover the core elements of CBT: psychoeducation, cognitive restructuring, and behavioral activation. In addition to the digital program, as a part of the Joyable product, all participants will be assigned a coach. The role of the coach is to provide accountability, motivation, emotional support, and guidance, leading clients to get the most out of the iCBT program. They provide this support through a combination of phone, text, and email interactions determined by the client. Joyable coaching is defined by 3 pillars: Motivational Interviewing (MI), Program Knowledge, and Client Experience. All coaches are trained to competency in MI, an evidence-based method for structuring conversations to harness a person's intrinsic motivation to change. MI has been shown to increase engagement and improve client outcomes. Coaches attend a rigorous 1-month training course, biweekly booster sessions, and submit tapes of client communications until they reach competency. In addition to MI, coaches are trained in the iCBT program and how to support clients with obstacles that may arise and effectively deliver program knowledge to drive client success. At the time of study enrollment, we will assist the subject in scheduling their first contact with their assigned coach.

72 Hour Telephone Encounter

Subjects will be contacted by the study team in person or by telephone 72+/- 24 hours after enrollment to troubleshoot any technical difficulties accessing the Joyable program.

30 Day Telephone Encounter

Subjects will be contacted by the study team phone or in person at 30 days +/- 7 days after enrollment to assess technical difficulties using the Joyable program, functional status using the modified Rankin scale, and quality of life using the Euroqol EQ-5D.

90 Day In-person Visit

Subjects will be seen by the study team 90 days +/- 14 days after enrollment to assess their neurologic function using the NIHSS, mood using the PHQ-9, functional status using the modified Rankin Scale, Quality of life using the Euroqol EQ-5D,^{20, 21} healthcare utilization using the Stanford Health Utilization survey,²² whether any other treatment for mental health problems was received (including medication and psychotherapy) and perceived utility of Joyable iCBT for depression as well as perceived barriers to successful use of internet-based CBT.

Table 1. Study measures and timing of assessment

	Baseline	72 hr Call	30 day call	90 day visit
Demographics	X			
Stroke information	X			
SSRI Use	X		X	X
Assess for technical problems		X	X	
NIHSS	X			X
mRS	X		X	X
EQ-5D	X		X	X
SHU				X
PHQ-9	X			X
Semi-Quantitative assessment of perceptions about Internet-based CBT				X

NIHSS=National Institute of Health Stroke Scale, EQ-5D=Euro-Qol 5D, SHU=Stanford Health Utilization survey, PHQ-9=Patient Health Questionnaire 9,

Analysis Plan

The baseline demographic variables of the study population will be summarized using means, medians, and proportions as appropriate. For each subject, we will calculate the total amount of time spent interacting with the Joyable program and the total number of Joyable activities that the patient successfully completed. We will then calculate averages across the study population. These metrics will provide important information on the average “dose” of CBT received. In an exploratory analysis we will look for relationships between baseline clinical and demographic factors and number of activities completed.

We will calculate the average PHQ-9 score at enrollment and 90 days. We will compare the PHQ-9 score from enrollment to day 90. The statistical power of this test is uncertain. In Table 2 we present estimated study power (with $\alpha=0.05$) across a range of assumptions about both the change in PHQ-9 over time and the standard deviation of the difference in PHQ-9 over time. These calculations show that although this is a small pilot study, we have >80% power to detect a difference in PHQ-9 of 3 or more points across a range of assumptions. The PHQ-9 will also be administered to subjects weekly via through the Joyable program. We will examine whether there are significant changes in score over time using repeated measures analysis (generalized estimating equations, GEE) with PHQ-9 score as the dependent variable and week as the independent variable.

In an exploratory analysis, we will divide patients into two groups based on PHQ-9 at study completion (*high depression symptoms*, defined as median or above and *low depression*

symptoms, defined as below the median score). Healthcare outcomes, including modified Rankin scale, health related quality of life, and healthcare utilization will be compared across groups. We hypothesize that patients with high depression symptoms will have worse functional outcome, lower quality of life, and higher healthcare utilization. We will also divide patients into groups based on their participation in the Joyable program and compare outcomes (e.g., PHQ-9 score, quality of life, health utilization) between subjects who showed high engagement in the program and those who showed low engagement.

Table 2. Statistical Power for single sample paired t-test

SD of the Difference	Difference in PHQ-9 Pre/Post Treatment				
	1	2	3	4	5
2	61%	99%	100%	100%	100%
3	32%	85%	99%	100%	100%
4	20%	61%	92%	99%	100%
5	15%	43%	77%	95%	99%
6	12%	32%	61%	85%	96%

Data Confidentiality

Internet-based files will only be made available to personnel involved in the study through the use of access privileges and passwords. Paper-based records will be kept in a locked, secure location and only accessible to study personnel. Prior to access to any study-related information, personnel will be required to sign statements agreeing to protect the security and confidentiality of identifiable information. Whenever feasible, identifiers will be removed from study-related information.

No clinical information obtained by the research team will be sent to Joyable. De-identified data from Joyable will be sent to the research team, which will include the number of Joyable activities completed by the subject, the number coaching interactions, and results of Joyable administered PHQ-9 and satisfaction assessments. This data will be organized by subject identification number, which can be used to link to the data collected by the research team. The research team will maintain a password protected file on a secured computer at the University of Pennsylvania which will link subject identification number to identifying information for each subject (name, medical record number, date of birth). Access to this file at the University of Pennsylvania will be limited to the PI and the study research coordinator. A Microsoft Excel document will be created which will include subject name, date of birth, and study identifier. This document will be uploaded to Penn+Box. The study team at Joyable will be given access to the file via Penn+Box. They will use this information to link the Joyable data elements described above to each subject. Joyable will then upload a Microsoft Excel file containing this data and subject identifier to the study Penn+Box, where it will be downloaded by the research team.

Patients who enroll in the study will all be participating in Joyable's iCBT Program for Depression. During enrollment in the study, patients will create an account with Joyable. As a part of this process, subjects register with Joyable using the same process as they currently use for their commercially available program. Registration requires the subject to submit the following PHI: name, date of birth, gender, and email address. Access to PHI will be limited to those who need it. This may include the individual coach who is assigned to each subject, coach managers who have access to subject data for the coaches that report to them, Joyable's analytic team which

has access to data for the purpose of aggregating and sharing back results to the research team, and a small number of engineers who can access data in order to troubleshoot bugs in the software. Subject interactions with Joyable will be governed by Joyable's existing Privacy Policy (see <https://joyable.com/privacy>) and terms of use (see <https://joyable.com/terms>).

Additionally, subjects will be given the option to opt in or out of email and text based coaching services. Joyable encrypts the transmission of personal information or uses Secure Socket Layer technology when possible. Joyable does not encrypt the transmission of text or email communication. This is made clear to the subject at the time of opt-in:

An important note on privacy:

Your privacy is important to us. Text messages and emails from your coach are not encrypted while in transit. To reduce the chance that your information is seen by the wrong recipient, we suggest you enable the highest security measures on your personal device (pass codes, strong passwords, 2 step authentication, etc). Taking these precautions will not eliminate all risks associated with communications sent in unencrypted text messages or email.

By checking the box above, you are agreeing to the risks associated with unencrypted text and email and consent to communicating with your Joyable coach through text and email, or Skype and email if you live outside of the United States.

Joyable meets or exceeds all federal requirements for protecting personal health information (PHI) of individuals under the Health Insurance Portability and Accountability Act of 1996 (HIPAA). All Joyable services operate behind a virtual private cloud with dedicated instances, and Joyable encrypts all PHI both in transit and at rest. Access to sensitive information is limited to Joyable employees directly involved with supporting any given client. Joyable participates in regular security assessments of both its processes and technology.

Subject Confidentiality

All data recorded will be kept in a spreadsheet that is managed by a member of the study team. This excel spreadsheet will be password protected and we will ensure that the access to this database is secured. Subjects will be coded using a study identification number that is detached from the patient's name and recorded into a separate excel spreadsheet. All study related paper files will be stored in a locked cabinet and accessible only by research staff. No published or presented materials will identify subjects by names, initials, or other means. The data set will be password protected and only accessible to the study team. If needed for future research this dataset will not be used without prior IRB approval.

Subject Privacy and Protected Health Information/Data Protection

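### The enrollment window is printed as 63 months in three places, while the objective and description concern recent stroke, which is never defined; the two need to be reconciled.

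*Combined protocol and SAP*

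**What the plan says.** The time limit appears three times, always with the same figure:

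- Study Design: "Adults (18 years or older) with ischemic stroke will be enrolled within 63 months of their event".
- Target Population: "Adult patients hospitalized with ischemic stroke within the past 63 months".
- Inclusion Criteria: "Acute ischemic stroke within the past 63 months".

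The question is framed differently. Objective 1 reads "Determine the feasibility of internet-based CBT in patients with recent ischemic stroke and depressive symptoms", and the Brief Description refers to a "telephone/email based coaching service in patients with recent stroke". No number is attached to the word recent anywhere, and no other inclusion or exclusion criterion bounds time since stroke.

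Under Accrual the plan says: "Due to the broad inclusion criteria of this study, it is expected that many of the patients seen, both inpatient and outpatient, will be eligible". Recruitment covers the inpatient service and outpatient clinics, and the clinics include second opinions for patients treated elsewhere.

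The date of symptom onset is recorded at Baseline CRF item 9. The Analysis Plan does not name time since stroke as a factor in any analysis.

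**The concern.** This is an eligibility limit that staff apply directly, and nothing else in the documents corrects or tightens it. Followed literally, it lets one sample contain people still in hospital after their stroke and people about five years past it.

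The design cannot sort this out afterwards. There is one arm, there are 20 subjects, and one of the two primary outcomes is change in PHQ-9 from enrollment to day 90. Without a control group, spontaneous change in mood is not separated from change due to the program, and it may not be the same early and late after stroke. Adherence could also differ with time since stroke. If a sizeable part of the sample is late, a conclusion worded for recent stroke would rest partly on people to whom that word does not apply.

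**Working it through.** **1. The window.** It is a stated limit, not a derived quantity, so there is no formula to reproduce. Converted: 63 months / 12 = 5.25 years.

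**2. The statements side by side.** Three places give 63 months and no place gives another figure. Two places say recent and give no figure. So the mismatch is between a number and an undefined word, not between two numbers. The Target Population line sides with the number.

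**3. Does other text settle which was meant?** No.

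- Some wording suits enrollment soon after stroke. The inclusion criterion says acute stroke. The psychotherapy exclusion covers only therapy before the stroke. Baseline CRF items 15 to 17 ask about work, medication and therapy before the stroke, and item 21 asks about discharge from the acute hospitalization.
- Other wording suits a long window. The criteria are called broad, and outpatients and second-opinion consultations are included.

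**4. How many late enrollees?** The documents give no split between inpatients and outpatients. The number could lie anywhere from 0 to most of the 20.

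**5. Accrual.** The inputs are "annual case volumes of approximately 600 strokes per year on the inpatient stroke service" and an expected 1 to 2 enrollments per week, complete within 6 months.

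- 20 / 2 = 10 weeks and 20 / 1 = 20 weeks, so the stated rate fits the 6-month plan.
- Assuming constant volume, a 63-month window spans 600 × 5.25 = 3,150 inpatient strokes, before deaths and every other criterion.
- New admissions over the 6-month enrollment period alone would be 600 × 0.5 = 300, and 20 / 300 = 6.7%. The documents do not say what fraction would meet the PHQ-9, language, internet and consent requirements, so this does not show that a shorter window would be enough.

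**6. Power.** Table 2 depends on the difference, its standard deviation, the sample size and alpha, and the window is not an input. For example, with a difference of 3, an SD of 4, n = 20 and a two-sided normal approximation: 3 × √20 / 4 = 3.354; 3.354 − 1.960 = 1.394; power = 91.8%, against 92% printed. Nothing in the table moves if the window is corrected.

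**7. What the analysis would show.** The Analysis Plan has an exploratory look at baseline clinical and demographic factors against activities completed. Time since stroke could be included there but is not named. No counterpart is planned for PHQ-9 change, and the repeated-measures model has week as its only stated independent variable.

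**The case against.** The strongest answer is that the figure may not be a rule at all. Two digits from an edit could have run together, in the source document or when the PDF was read, and an edit to the window would have been made in every place it appears. Identical printing three times is therefore no proof of intent. This stands. It is why the point asks for confirmation and names no correct window. It does not dispose of the point, because nothing in the text supplies a different figure.

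Second, the long window may be deliberate. Target Population matches it and Accrual calls the criteria broad. This also stands as a possibility; in that case it is the word recent that needs to change.

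Third, the sample may turn out mostly recent. That is true: the rule permits late enrollment without requiring it.

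A reader might infer more than this, in three ways that the documents do not support:

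- That the rule fails to deliver the trial's population. The plan's own Target Population line agrees with the rule, and recent is undefined.
- That a mixed sample would make the results uninterpretable. Activities completed is a directly observed count that remains valid for whoever was enrolled. The documents give no figure for how recovery of mood differs between early and late stroke. Spontaneous change would affect any single-arm pre/post comparison, including one with a narrow window.
- That the ratio of the window to the 90-day follow-up measures the harm. It compares unrelated quantities and says nothing about bias.

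**Conclusion.** The inconsistency is real and worth correcting, in a limited form. As printed, eligibility extends to 5.25 years after stroke while the stated question is about recent stroke, so the results could not be clearly attributed to recent stroke if late enrollees are present. The size of the effect cannot be given: the share of late enrollees is unknown, and the documents hold no data on PHQ-9 change or adherence by time since stroke. Power and sample size are unaffected.

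The conclusion assumes that the printed figure is the one staff would use. If it proves to be an artefact of editing or of reading the PDF, only the correction of the figure and a definition of recent remain to be done.

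**What to change.** 1. The sponsor confirms the intended window and makes Study Design, Target Population and Inclusion Criteria agree with the objective. Either the figure is corrected in all three places, or, if 63 months is intended, the word recent is removed from Objective 1 and the Brief Description. If the word is kept, it should be given a number.
2. If the long window stands, add a description of activities completed and PHQ-9 change by time since stroke, as a scatter plot or a simple listing. With 20 subjects this should be descriptive only, without subgroup tests. Time since stroke is the screening PHQ-9 date minus the onset date at Baseline CRF item 9, so no new data are needed.

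**Cost.** If the figure is a misprint, or if only the objective and description change, this is a wording correction. The description in step 2 needs one figure or listing. If 63 months has been the operating rule and is now narrowed, that is a change of eligibility: the pool shrinks, and the estimate of 1 to 2 enrollments per week, which rests on broad criteria, must be rechecked rather than carried over.
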